## Statistical Analysis Plan

The sample size was determined using the mean difference formula:  $n = (Z\alpha / 2 + Z\beta) 2 * 2 * \sigma^2 / d^2$  a reduction in GV was estimated from 4.85 to 2.2 with an expected standard deviation of 2.8 in the MAGE index according to RR. Henry et al. [19] with an alpha value of 0.05 and a power of 0.80, resulting in a sample size of 88 subjects, with 44 subjects in each treatment group.

Patient recruitment began in October 2019 and was interrupted due to the SARS-COV-2 pandemic in March 2020. Nevertheless, patients who were already enrolled were followed up. Recruitment was normally restarted in March 2021; one of the inclusion criteria was adjusted, allowing HbA1c <13.0%, prior limit <12.0%. The last patient was recruited on December 6th, 2021. The complete study was concluded in March 2021.

A total of 88 patients met the selection criteria, signed the informed consent, and were randomized 1:1 on [www.randomization.com](http://www.randomization.com) (complete list of it is showed as supplementary material) to receive daily either DAPA 10 mg + MET 2000mg or MET 2000mg for 12 weeks. Both groups were monitored for GV using a CGM system for 7 days at baseline (W0) and on week 12 (W12).

Pre-randomization: patients were given 2000mg of MET daily for two weeks, only patients who tolerated this dose were included in the study and a treatment was randomly assigned.

Treatment: subjects who met the pre-randomization period and tolerated treatment were randomized 1:1 to receive either DAPA 10 mg/day + MET 2000 mg/day or MET 2000 mg/day for 12 weeks.

Of the total of 264 patients surveyed, a sample of 88 met the inclusion criteria and none of the exclusion criteria randomization DAPA+MET n=42 and MET n= 46. During the study, 7 patients discontinued (DAPA+MET n=1 and MET n=6). 80 patients concluded the study for 12 weeks (DAPA+MET n=41 and MET n=39). One patient was removed from the study (MET n=1) because he did not comply his medication intake nor the instructions during CGM. Study flowchart is displayed in Figure 1.

The baseline characteristics were, the age [53.7  $\pm$  8.6 years DAPA+MET versus 50.9  $\pm$  11.8 years MET; p=0.2], TIR% Target: 70-180 mg/dL [55.5% (12.6-80.6) DAPA+MET versus 82.7% (26.1-95.1) MET; p=0.02], BMI [30.9  $\pm$  6.9 kg/m^2 DAPA+MET versus 30.1  $\pm$  3.2 MET; p=0.24], glucose [202.4  $\pm$  70.5 mg/dL DAPA+MET] versus 179.0  $\pm$  62.9 mg/dL MET; p=0.11], insulin [12.2  $\pm$  13.3  $\mu$ U/mL DAPA+MET versus 10.9  $\pm$  6.6  $\mu$ U/mL MET; p=0.57]. Complete baseline characteristics of the subjects included are summarized in Table 1.

All the measurements were carried out fasting. Student's T test was performed for normal variables to obtain significance. Skewed distribution variables are expressed with median and interquartile values of 25% and 75%, significance for these variables was obtained with the Mann Whitney U test.

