Does the protocol involve the handling and labeling of biological samples? If applicable, mention the procedures that will be used

Yes, with the patient's initials, date of birth, internal laboratory patient number, and randomization number.

Information to ensure that obtained biological samples will not be used for permanent or immortal cell lines or purposes unrelated to the study

Qualified personnel will take samples for this activity and will be processed within the institution. Samples will not be sent to any other institution/company, so there is no risk of being used for purposes other than those stipulated in the protocol.

Description of treatment groups

Included subjects will be randomized 1:1 to receive:

- **Group 1:** Dapagliflozin 10 mg/day + Metformin 2000 mg/day and, if necessary, as mentioned previously, rescue treatment.
- **Group 2:** Metformin 2000 mg/day and, if necessary, as mentioned previously, rescue treatment. Treatments will be administered for 12 weeks. Patients who do not tolerate Metformin at a dose of 2000 mg will have their dose adjusted to 1500 mg daily. If patients do not tolerate 1500 mg daily, the dose will be titrated to 1000 mg daily. If they do not tolerate this dose, they will be withdrawn from the study.

Mechanisms for treatment assignment

The <https://www.google.com/search?q=randomization.com> tool will be used (The Table is attached as Appendix 1 of the protocol).

If a placebo group is used, include its justification

Not applicable

Criteria for premature withdrawal from the study

- Allergic reaction to any of the study medications or their excipients.
- Patients who do not tolerate Metformin 1000 mg/day.
- Severe life-threatening illness.
- Pregnancy during the study.
- Presence of acute renal failure (decrease in > 40% of glomerular filtration rate).
- Lactic acidosis or ketoacidosis.

Procedures for withdrawing a patient from the study

The patient will be notified of withdrawal from the protocol and will receive standard treatment, according to AACE 2019 guidelines (MET, GLP1 agonist, SGLT2 inhibitor, DPP4i, acarbose, thiazolidinediones, insulin, or sulfonylurea) and will be referred for follow-up at the secondary care level.

Criteria for premature (partial or complete) suspension of the study

NA

Selection Criteria

a) Inclusion criteria

- Subjects > 18-77 years old.
- Both men and women.
- HbA1c \geq 7.7% <12% (HbA1c from 9 to <12%: without catabolic symptoms).
- BMI $>$ 25 kg/m².

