- Diagnosis of T2D: if a patient has taken any drug and/or insulin, they will be prescribed only Metformin as a washout period in the pre-randomization phase for 2 weeks.

b) Exclusion criteria

- Complications related to T2D and catabolic symptoms.
- HbA1c $>$ 9% with catabolic symptoms.

- CKD-EPI creatinine clearance: <60 ml/min.
- LADA or T1D.
- Concomitant clinically significant disease such as: liver, hematological, oncological, psychiatric, or rheumatic disease.
- Symptoms of markedly uncontrolled diabetes: (marked polyuria or polydipsia + 10% weight loss within the last 3 months before enrollment).
- Known hypersensitivity to dapagliflozin, metformin, or any of the drug excipients.
- Unstable or rapidly progressing kidney disease.
- Patients with severe liver failure (Child-Pugh class C).
- Patients with bariatric surgery.
- Any major CV event / vascular disease within 3 months before signing consent at enrollment, as assessed by the investigator.
- For women only: currently pregnant (confirmed with a positive pregnancy test) or lactating.
- Being hospitalized or having less than one month since hospital discharge.

c) Elimination criteria

- Allergy to dapagliflozin, severe life-threatening illness, or pregnancy during the study.
- Patients presenting with acute renal failure (decrease in > 40% of GFR)
- For women only: pregnancy confirmed with serum chorionic gonadotropin. In case of pregnancy during the study, the subject must be eliminated from the trial, offered standard treatment indicated in point 36, and the Pregnancy Outcome Report (Annex) must be completed to record essential details of the mother. Part I should be completed after pregnancy identification and Part II is to record the pregnancy outcome.

39. Outcomes and Variables

- **Primary Variable:** Change from baseline in GV (MAGE) in mg/dL after 12 weeks of treatment between the DAPA+ MET group versus the MET monotherapy group.
- **Secondary Variables:**
 - Change from baseline (absolute difference) in HbA1c levels (%) after 12 weeks of treatment between the DAPA + MET group versus the MET monotherapy group.
 - Change from baseline (total difference) in insulin levels (μ U/mL) after 12 weeks of treatment between the DAPA + MET group versus the MET monotherapy group.
 - Change from baseline (absolute difference) in oxidative stress measurement (total antioxidant capacity) after 12 weeks of treatment between the DAPA + MET group versus the MET monotherapy group.

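### Randomised patients are removed for post-randomisation events with no analysis set or missing-data method stated, and 1 of 42 versus 7 of 46 did not complete, with a reason given for only one

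*SAP*

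**What the plan says.** **Protocol, removal rules.** Two lists govern removal after randomisation.

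- *Criteria for premature withdrawal from the study* begins with "Allergic reaction to any of the study medications or their excipients". It also covers metformin intolerance, serious illness, pregnancy, renal failure and acidosis. *Description of treatment groups* says of patients who still cannot take metformin after two permitted dose reductions: "If they do not tolerate this dose, they will be withdrawn from the study".
- *Selection Criteria, c) Elimination criteria* has "Allergy to dapagliflozin, severe life-threatening illness, or pregnancy during the study" and "Patients presenting with acute renal failure (decrease in > 40% of GFR".

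Under *Procedures for withdrawing a patient from the study*, these patients go to standard treatment and are referred to secondary care. Nothing provides for the end-of-treatment CGM, which is placed at Visit 5 DP and removed at Visit 6 DP.

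**Protocol, analysis.** *Statistical Analysis* excludes patients with an acute stress event, because of its effect on GV, and does not define the term. No analysis population or missing-data method is given.

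**SAP, participant flow.** The text reports "randomization DAPA+MET n=42 and MET n= 46", then "During the study, 7 patients discontinued (DAPA+MET n=1 and MET n=6", then "80 patients concluded the study for 12 weeks (DAPA+MET n=41 and MET n=39". No reasons are given for the seven discontinuations. The remaining loss is explained: "One patient was removed from the study (MET n=1) because he did not comply his medication intake nor the instructions during CGM". The SAP names no analysis set and no method for missing outcomes.

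**The concern.** The primary variable is the between-arm comparison of change in MAGE over 12 weeks. Randomisation supports that comparison for everyone randomised. It supports a comparison of those who finished only if finishing is unrelated to outcome, and nothing in the documents lets a reader judge that.

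Three features make the question a real one:

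- Stopping study drug is treated as leaving the trial, so tolerance and adherence help decide who has a week-12 value.
- One MET patient was removed for a reason that appears in neither protocol list, in a trial where allocation was open.
- The acute-stress exclusion has no definition, so it too can be applied with the arm and perhaps the CGM trace in view. The SAP does not say how many patients it removed, if any.

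At stake is bias in the primary estimate. The losses fall mainly in the comparator arm and are almost entirely unexplained.

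**Working it through.** **1. Reproduce the flow.** Inputs are from the SAP.

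- DAPA+MET: 42 − 1 = 41.
- MET: 46 − 6 − 1 = 39.
- Total: 41 + 39 = 80 = 88 − 7 − 1.

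The reported counts close.

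**2. Non-completion by arm.**

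- DAPA+MET: 1/42 = 2.4%. MET: 7/46 = 15.2%. Overall: 8/88 = 9.1%.
- Difference: 15.2 − 2.4 = 12.8 percentage points (95% Newcombe interval 0.3 to 26.0). Fisher exact two-sided p = 0.060.
- Counting only the seven discontinuations (1/42 versus 6/46), Fisher p = 0.11.

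The imbalance is therefore borderline as a statistical finding. One of the eight losses has a stated reason.

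**3. Check that reason against the lists.** Poor medication intake and failure to follow CGM instructions appear neither in the withdrawal criteria nor in the elimination criteria.

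**4. Compare the two allergy rules.** The elimination list names dapagliflozin only, which Group 2 does not receive. The withdrawal list covers any study drug. The two are not the same rule.

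**5. Size of a possible bias.** Let *d* be the difference in mean MAGE change between lost patients and completers in an arm. The all-randomised mean is the completer mean plus (fraction lost) × *d*. The between-arm difference therefore moves by:

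- (7/46 − 1/42) × *d* = 0.128 × *d* if lost patients differ in the same direction in both arms;
- (7/46 + 1/42) × *d* = 0.176 × *d* if the directions are opposite.

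The documents give no value for *d*. The values below are assumptions. The middle one is the MAGE decrease that the protocol's *Background* cites from the dapagliflozin CGM trial.

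| Assumed *d* (mg/dL) | Shift in MET mean (7/46 × *d*) | Shift in difference, same direction | Shift in difference, opposite |
|---|---|---|---|
| 5 | 0.8 | 0.6 | 0.9 |
| 15.3 | 2.3 | 2.0 | 2.7 |
| 30 | 4.6 | 3.9 | 5.3 |

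**6. The same check in SD units.** For *d* of 0.25, 0.5 and 1 SD (assumed), the shift is 0.03, 0.06 and 0.13 SD in the same direction, or 0.04, 0.09 and 0.18 SD in opposite directions. The planned effect is 2.65/2.8 = 0.95 SD.

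**7. Power is not the issue.** On the plan's own inputs (difference 4.85 − 2.2 = 2.65, SD 2.8, two-sided 0.05):

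- With 41 and 39, the SE is 2.8 × √(1/41 + 1/39) = 0.626 and power is 98.8%.
- With 42 and 46, the SE is 0.598 and power is 99.3%.

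**The case against.** **The stronger reading.** A reader might infer that the removal rules, and in particular an allergy criterion that only Group 1 can meet, produced the 1/42 versus 7/46 split. The documents do not support that. No reason is given for seven of the eight losses, which could be withdrawn consent or loss to follow-up. A criterion that only Group 1 can meet can remove patients only from Group 1, yet the excess is in MET. The withdrawal list also covers allergy to any study drug. This part of the objection stands in full.

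**Tolerance was screened beforehand.** The SAP says only patients who tolerated metformin 2000 mg for two weeks were randomised, and the protocol allows two dose reductions before withdrawal. Both limit loss through intolerance, and no loss is documented as intolerance. That stands, but it leaves the seven losses unexplained.

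**The bias is modest and its size is assumed.** This is also right. At *d* = 15.3 the shift is 12.8% of the cited decrease, but that percentage is just the gap in loss rates and adds no information about MAGE. Nor does the protocol say whether the cited decrease is net of placebo.

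**The flow sentence is a report and not an analysis rule.** True: a completer analysis is inferred from the 80 who finished and the absence of follow-up after withdrawal. Neither document states it. But no other population is named, and that gap is the point.

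**The trial is over.** The SAP describes the study as concluded, so new protocol wording cannot recover missed visits. This narrows the remedy mostly to analysis and reporting.

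**Conclusion.** The point holds and should be fixed. Randomised patients leave the trial or the analysis because of what happens after randomisation. One was removed for a reason the protocol does not list, in an open-label trial. No analysis set or missing-data method is stated. Non-completion was 2.4% versus 15.2%, with one reason given for eight losses. A completer comparison of MAGE change under these conditions is not protected by randomisation.

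The likely size is moderate: about 0.6 to 3.9 mg/dL on the between-arm difference if lost patients differ in the same direction in both arms, and 0.9 to 5.3 mg/dL if in opposite directions. Both ranges rest on an assumed 5 to 30 mg/dL difference between lost patients and completers. The direction of bias is unknown. On the SD scale the shift is small beside the planned effect, so this alone would be unlikely to overturn an effect of that size; it would matter more if the observed effect is smaller. The documents do not establish what caused the imbalance.

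**What to change.** **In the SAP**

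- Make the primary analysis all randomised patients in their assigned arm (42 and 46).
- Restore the removed MET patient with any usable CGM data. If there are none, treat his week-12 MAGE as missing.
- Drop the acute-stress exclusion from the primary analysis. If it is kept as a sensitivity analysis, define the event and report how many patients it affects in each arm.
- State a method for missing week-12 MAGE, for example multiple imputation by arm using baseline MAGE and the protocol's ANCOVA covariates (age, sex, BMI, baseline HbA1c, time since diagnosis). Add a delta-shift sensitivity analysis over 5 to 30 mg/dL, with the shift in the same and in opposite directions across arms.
- Report reasons for discontinuation by arm, and show the completer result (41 and 39) as a sensitivity analysis.

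**In the protocol**

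- In the withdrawal and elimination sections, separate stopping study drug from leaving the trial, so that willing patients keep the Visit 5 and Visit 6 assessments. This helps only where follow-up is still possible.
- Reconcile the two allergy criteria. The clinical stopping rules themselves are left as they are.

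**Cost.** Wording and a little more analysis. The protocol already has a route for departures from the statistical plan, a letter to the research committee. Because participant flow and baseline data are already known, the change should be dated and declared as made after those data were seen. The estimate may be slightly diluted by any off-treatment values.

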STATISTICAL ANALYSIS. Quantitative variables with normal distribution according to the Kolmogorov-Smirnov test will be expressed as Means \pm Standard Deviation. Quantitative variables with non-normal distribution will be expressed as Medians (Interquartile Range 25-75). Categorical variables will be expressed as proportions (percentages). Change deltas will be calculated for each group and compared using ANCOVA, considering age, sex, BMI, baseline HbA1c, and time since Diabetes diagnosis as covariates. A p-value \leq 0.05 will be considered significant. All analyses will be performed with SPSS 22.0.

Study Timeline

Study Type	Select an option
Retrospective	
Prospective	X

Process of assigning study groups

Maneuver	Yes (Include corresponding information)	No	Not applicable
Randomization	X		
Open-label study	X		
Single-blind study		X	
Double-blind study		X	
Triple-blind study		X	

Description of maneuvers or interventions

- **Clinical History:** Will be conducted via telemedicine (Phone call/Videocall, Whatsapp, Teams, Zoom, Google Forms) at visit 1 DP of the treatment period.
- **Diet Plan Prescription:** Will be conducted via telemedicine (Phone call/Videocall, Whatsapp, Teams, Zoom, Google Forms) at visit 2 DP of the treatment period.
- **Anthropometric Measurements and Physical Exam:** Will be performed at visits 1 DP, 3 DP, 4 DP, and 6 DP of the treatment period.
- **GV Monitoring:** Both groups will be monitored before treatment and at the end. The iPro™ CGM system (Medtronic, Northridge, CA) will be used. Baseline continuous glucose monitoring will begin in week 1 (Visit 1DP) and end seven days later at Visit 2DP (day 1, Week 2). End-of-treatment continuous glucose monitoring will begin at Visit 5 DP (week 12) and end 7 days later (Visit 6 DP).
- **Measurement of HbA1c and Insulin Levels:** Will be performed at visits 1DP and 6DP of

the treatment period.

- **Spot Urine Sample:** Will be collected at Visits 1DP, 3DP, 4DP, and 6DP.
- **Measurement of Oxidative Stress and Inflammation Biomarkers:** Will be performed at visits 1DP, 3DP, 4DP, and 6DP of the treatment period.
- **WHO Physical Activity Questionnaire:** Will be evaluated via telemedicine (Phone call, Whatsapp, Teams, Zoom, Google Forms) at visits 1DP, 3DP, 4DP, and 6DP of the treatment period.

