- Change from baseline (total difference) in the measurement of inflammation biomarkers (VCAM-1 and adiponectin) after 12 weeks of treatment between the DAPA + MET group versus the MET monotherapy group.
- Change from baseline (absolute difference) in body fat quantification after 12 weeks of treatment between the DAPA + MET group versus the MET monotherapy group.
- Change from baseline (total difference) in the parameters of cardio-metabolic risk factors (weight (kg), total cholesterol (mg/dL), HDL (mg/dL), LDLc (mg/dL), albuminuria (mg/mg creatinine), and blood pressure (mmHg)) after 12 weeks of treatment between the DAPA + MET group versus the MET monotherapy group.

Methods to be used to contact patients

Personal contact data such as landline and mobile phone numbers, email address will be obtained via Phone call/Videocall, Whatsapp, Teams, Zoom, or Google Forms. Due to the SARS-CoV-2 pandemic, investigators will conduct home visits and/or collect data and hold medical consultations via Phone call/Videocall, Whatsapp, Teams, Zoom, or Google Forms.

Statistical Analysis (Description of the information processing and presentation plan. Include justification for the statistical tests to be used)

Stratified randomization in both groups to balance patient types and control potential bias. The normality of variables will be analyzed using the Kolmogorov-Smirnov test. According to the distribution of variables, they will be expressed as mean and standard deviation (SD) or median and interquartile range (IQR) for normally or skewed distributed variables, respectively. GV will be determined using the MAGE index. Comparison between the two groups will be evaluated using ANCOVA. A p-value based on two-tailed tests ≤ 0.05 will be considered significant. All analyses will be performed with SPSS 20.0 (Chicago, IL). Patients experiencing an acute stress event during the study will be excluded from the analysis due to the impact on GV.

Justification of sample size (include study power and the p-value considered significant)

The sample size was determined using the difference of means formula:

$$n = (Z\alpha / 2 + Z\beta)^2 * 2 * \sigma^2 / d^2,$$

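### Insulin change is to be compared on the raw scale without baseline insulin as a covariate, although the SAP's own figures (12.2 ± 13.3 µU/mL) show right skew or an extreme value; the likely cost is power on a secondary endpoint

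*SAP*

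**What the plan says.** **Baseline reporting (SAP, Statistical Analysis Plan).** The insulin entry reads "insulin [12.2 $\pm$ 13.3 $\mu$ U/mL DAPA+MET versus 10.9 $\pm$ 6.6 $\mu$ U/mL MET; p=0.57". The tests described with the baseline data are a Student's "T test was performed for normal variables to obtain significance" and, for the others, "Skewed distribution variables are expressed with median and interquartile values of 25% and 75" percent, where "significance for these variables was obtained with the Mann Whitney U test". Of the variables given in the text, only time in range is shown as median and quartiles.

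**Normality check (Protocol, Statistical Analysis).** "The normality of variables will be analyzed using the Kolmogorov-Smirnov test". Both here and under Methods, the result decides only whether a variable is summarised as mean and SD or as median and IQR.

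**Endpoint comparison (Protocol, Methods, STATISTICAL ANALYSIS).** "Change deltas will be calculated for each group and compared using ANCOVA, considering age, sex, BMI, baseline HbA1c, and time since Diabetes diagnosis as covariates". HbA1c is the only laboratory value whose baseline is a covariate. No transformation, outlier rule or residual check is given.

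**Endpoint definition (Protocol, Definition of Follow-up Variables, repeated under Outcomes and Variables).** Insulin is a secondary variable, defined as change from baseline in µU/mL. The Sample Size section states that secondary variables were not allowed for in the calculation.

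**The concern.** Insulin cannot be negative, so an SD larger than the mean rules out anything close to a normal distribution. Either the whole distribution has a long right tail, or one or two values are extreme. In both cases the difference between two raw measurements tends to have heavy tails, and a few patients can set both the estimated arm difference and its standard error.

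The planned comparison does nothing to limit this. The normality test changes the display of a variable but not its analysis. ANCOVA is applied to the raw change in every case, and the patient's own starting insulin, normally the strongest predictor of the change, is not in the model.

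At stake is the chance of detecting a real effect on insulin with 80 completers, for an endpoint that was never sized, and a difference in µU/mL that may describe a handful of patients more than the typical one.

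**Working it through.** **Inputs.** From the SAP: insulin 12.2 ± 13.3 (DAPA+MET) and 10.9 ± 6.6 (MET), p=0.57; 42 and 46 randomised; 41 and 39 completers. From the protocol: two-sided 0.05, raw change, no own-baseline covariate.

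**1. Reproduce the stated p-value.** The difference is 1.3.
- Student, n=42/46: pooled variance = (41×13.3² + 45×6.6²)/86 = 107.1; SE = √(107.1×(1/42+1/46)) = 2.21; t = 0.59; p = 0.558.
- Welch, n=42/46: SE = √(13.3²/42 + 6.6²/46) = 2.27; t = 0.57; p = 0.569.
- With n=41/39: 0.584 and 0.579.
- Rounding in the means and SDs allows 0.53–0.61.

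The stated 0.57 is therefore consistent with a raw-scale t test, though this does not prove one was used.

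**2. Is a normal summary tenable?** A normal model puts Φ(−12.2/13.3) = Φ(−0.92) = 17.9% of DAPA+MET values below zero, and Φ(−10.9/6.6) = Φ(−1.65) = 4.9% of MET values. It is not tenable in the first arm.

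**3. General skew or one extreme value?** Suppose 41 of the 42 DAPA+MET patients have SD 6.6, as in the other arm, and one does not. With d the distance of that value from the mean of the rest, (n−1)s² = (n−2)s₀² + d²(n−1)/n.
- d² = (41×13.3² − 40×6.6²)×42/41 = 5644, so d = 75.1.
- The rest average 12.2 − 75.1/42 = 10.4, and the single value is about 85.5 µU/mL.

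One value near 85 would produce the reported figures. Without it the arm difference changes sign (10.4 versus 10.9). A generally right-skewed distribution fits equally well.

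**4. Power by scale of analysis.** The documents give no insulin effect, correlation or distributional shape. I assume:
- lognormal data with the same log-SD in both arms, set to each reported CV in turn: log-SD = √ln(1+CV²), which is 0.885 for CV 1.09 and 0.56 for CV 0.61;
- 41 versus 39 patients;
- a proportional reduction of 25% or 30%;
- correlation r of 0.5 or 0.7 on the log scale.

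The results come from 4,000 simulated trials per row (standard error at most √(0.25/4000) = 0.8 points). The listed covariates were left out.

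| CV | r | Reduction | Raw change | Raw change + own baseline | Log ANCOVA + log baseline |
|---|---|---|---|---|---|
| 1.09 | 0.5 | 25% | 18% | 26% | 39% |
| 1.09 | 0.5 | 30% | 25% | 38% | 54% |
| 1.09 | 0.7 | 25% | 26% | 34% | 51% |
| 1.09 | 0.7 | 30% | 36% | 51% | 70% |
| 0.61 | 0.5 | 25% | 48% | 68% | 75% |
| 0.61 | 0.5 | 30% | 62% | 84% | 90% |
| 0.61 | 0.7 | 25% | 66% | 82% | 89% |
| 0.61 | 0.7 | 30% | 83% | 94% | 98% |

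Repeat simulations moved entries by up to about 2 points. With no true effect, all methods rejected in about 4–6% of trials.

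**5. Separate the two causes.** At CV 1.09, r=0.7 and a 25% reduction, adding baseline insulin lifts power from 26% to 34%, and moving to the log scale lifts it from 34% to 51%. Part of the loss is thus the missing covariate and part is the scale.

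**6. Vary the assumed effect.** For a 10% proportional effect the log scale gains only about 2–3 points over baseline-adjusted raw change. For an additive effect (25% of the mean, with additive noise of SD 4), the baseline-adjusted raw analysis has 85–87% power and the log analysis 73–76%: the log scale loses about 11–13 points.

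**The case against.** Several stronger readings are tempting, and the documents do not support them.

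- *The normality test picks the wrong endpoint analysis.* It does not pick the endpoint analysis at all. In the protocol it governs only how variables are expressed, so how often a Kolmogorov-Smirnov test would pass skewed data has no bearing on endpoint power.
- *Skewed endpoints will be compared by a rank test on changes.* The t test and Mann-Whitney sentences in the SAP accompany the baseline data. Nothing extends them to changes.
- *Insulin was demonstrably classed as normal.* The display and the p-value point that way, but only loosely. BMI is also shown as mean ± SD, and its p=0.24 is not reproduced by a t test from its own figures (0.48 Student, 0.49 Welch with n=42/46). A reporting slip is possible.
- *The other biomarkers are skewed too.* The text gives no distribution for VCAM-1, adiponectin or albuminuria. Even for insulin, skew at baseline does not prove skew in the change.
- *The log scale is always better.* Step 6 shows otherwise. The gain rests on a proportional effect and lognormal data, both assumed.

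It is also fair to say that type I error is sound, that secondary variables were openly left unpowered, and that the protocol defines the insulin endpoint in µU/mL, so replacing that measure after baseline data have been reported changes what is estimated.

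These arguments narrow the point to insulin and call for keeping the µU/mL result. They do not explain why a variable with an SD above its mean should be analysed untransformed and without its own baseline.

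**Conclusion.** The point holds for insulin, as a recommendation and not as a validity failure. Its firm part needs no assumption: the reported 12.2 ± 13.3 is incompatible with a near-normal distribution, and the planned raw-change ANCOVA has neither a transformation nor baseline insulin to limit the influence of a few high values.

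The size is conditional. Under the assumptions in step 4, log-scale ANCOVA with log baseline has about 15–34 percentage points more power than raw change without its own baseline, and about 4–19 points more than raw change with it. The advantage is largest at the DAPA+MET arm's CV. It nearly vanishes for a small effect and reverses for an additive one.

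A reader might infer inflated false positives or a threat to the main conclusion. Neither follows: rejection under no effect stayed near 5%, and MAGE is not involved.

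**What to change.** 1. Analyse insulin by ANCOVA of the log end-of-treatment value on log baseline insulin, arm and the covariates already listed. Report the ratio of geometric means with its 95% CI.
2. Keep the change in µU/mL, adjusted for baseline insulin, as a supporting analysis, because the protocol defines the endpoint in those units.
3. Inspect model residuals in both analyses, in place of relying on normality of the raw variable.
4. Report baseline insulin as median (IQR) or geometric mean.
5. Use the same log-scale approach for VCAM-1, adiponectin and albuminuria only if pooled data viewed without arm labels, or the residuals, show right skew. State beforehand how values at or below the detection limit enter the logarithm.

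The cost is SAP wording and a re-run on data already collected, plus the letter to the research committee that the protocol requires for deviations from the statistical plan. Because enrolment has closed and baseline data are reported, the date and reason for the change should be recorded. The downside is that the main insulin result becomes a ratio, which is less familiar than a µU/mL difference, and some power is lost if the true effect is additive.
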